**Briefly describe the proposed modification(s) and explain why each change is needed.**

I am seeing increased interest in my study, so to be safe I would like to increase the study sample size from 60 to 100. Given the benefit of the intervention and interest from the eligible community members, it seems fair to increase the sample size and not exclude any interested eligible members.

I am also increasing focus group number. We will ask for 8- 10 volunteers and divide them into two groups of 4-5 participants. As the sample size increases, I would like to make sure that focus group is representative of the sample as well, so I would like to increase focus group participants.

These changes have been made in the protocol as well.

\*required

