**Include sample size calculations, if applicable.**

Adults age 50 years or older, who are willing to participate will be recruited unless they have a significant cognitive or language barrier that will prevent them from successfully answering the study questionnaires.

We will use a randomized controlled trial (RCT) with waitlist control to determine the intervention's feasibility, acceptability, and initial efficacy. Although the proposed study is a feasibility pilot study, we will investigate the preliminary efficacy of the intervention. Therefore, the sample size for this current pilot study was estimated based on four repeated measurements: (baseline, right after intervention, post-intervention (at one month), and follow-up (at second month). Using an estimated effect size (Cohen's  $f= 0.2$ ), an alpha of 0.05, and a power of 90%, for a repeated measure ANOVA between-within effects, with two groups and four measurement time points, the sample size was determined to be 46. This sample size was then increased by 33% to allow for attrition, to give the total sample of 60. The sample size was determined using G\*Power (v. 3.1.9.7).

**Given the interest from the community, we are increasing our sample size to 100. We do not want to exclude eligible community members who might benefit from participating in the study. This will help increase the study power as well.**

\*required

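### Does the attrition allowance that takes 46 to 60 leave the trial short of its stated power?

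*Combined protocol and SAP*

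**What the plan says.** The section headed 'Include sample size calculations, if applicable' sizes the trial "for a repeated measure ANOVA between-within effects, with two groups and four measurement time points". It takes Cohen's f = 0.2 with "an alpha of 0.05, and a power of 90" percent, and G*Power returns 46 in total. The allowance for loss follows: "This sample size was then increased by 33% to allow for attrition, to give the total sample of 60". The section names no expected dropout rate.

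The next paragraph replaces 60: "Given the interest from the community, we are increasing our sample size to 100". It adds, of that increase, "This will help increase the study power as well". The modification summary makes the same request: "I would like to increase the study sample size from 60 to 100". The maximum number of subjects, the enrolment breakdown (50 and 50), the recruitment section and the description of study conduct all carry 100, or 50 per arm. The current target is therefore 100, and the step from 46 to 60 remains only as the history of the calculation.

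**The concern.** The sentence contains a percentage and a total that do not agree, and the percentage is the only attrition-related number in the sample-size text. Because its stated purpose is to cover attrition, a reader may take 33% as the loss the trial was built to withstand. On that reading the method is wrong as well as the sum. To keep n completers after losing a fraction d, one divides n by (1 − d); multiplying by (1 + d) gives too few.

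If 60 were the enrolment and a third dropped out, the trial would fall below the 46 on which its 90% power rests. Retention is also among the feasibility and acceptability outcomes listed under 'How will you conduct this study?', so a planning figure for loss could colour how observed retention is judged. The increase to 100 leaves the old sentence in place and gives no expected attrition, completers or power at the new size.

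**Working it through.** **Inputs.** From the sample-size section: f = 0.2, alpha = 0.05, power 90%, k = 2 groups, m = 4 measurements, 46 evaluable, a 33% increase, 60, and the current 100. The section does not state the correlation between repeated measures (rho) or the sphericity correction (epsilon). I assume rho = 0.5 and epsilon = 1 and give ranges below.

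**Step 1: reproduce 46.** For the within-between interaction in G*Power, lambda = f² × N × m × epsilon / (1 − rho), with df1 = (k − 1)(m − 1) × epsilon and df2 = (N − k)(m − 1) × epsilon. At N = 46, lambda = 0.04 × 46 × 4 / 0.5 = 14.72, with 3 and 132 degrees of freedom. Power is 0.903, and 46 is the smallest even N that reaches 90%. The plan's figure reproduces, which supports the two assumptions as the ones used.

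**Step 2: the inflation.**
- 46 × 1.33 = 61.18, so 62 for equal arms.
- 60 / 46 = 1.304, an increase of 30%.
- Attrition tolerated at 60: 1 − 46/60 = 23.3%.
- Attrition tolerated at 62: 1 − 46/62 = 25.8%.

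**Step 3: what a 33% increase protects against.** 1 / (1 − 0.25) = 1.333, so it is the correct inflation for a 25% loss. At 60 with 25% lost, 60 × 0.75 = 45 remain. Power is 0.895 at 45 against 0.903 at 46.

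**Step 4: the alternative reading, with 33% as a dropout rate.**
- Required enrolment: 46 / 0.67 = 68.7, so 69, or 70 for equal arms.
- At 60: 60 × 0.67 = 40.2, so 40 completers and power 0.852.

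**Step 5: the current target.**
- At 100, attrition tolerated before completers fall below 46: 1 − 46/100 = 54%.
- With 33% lost, 67 remain and power is 0.981.

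**Ranges.** Power on the four-measurement calculation:

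| Completers | rho 0.3 | rho 0.5 | rho 0.7 |
|---|---|---|---|
| 40 | 0.702 | 0.852 | 0.979 |
| 46 | 0.771 | 0.903 | 0.991 |
| 67 | 0.917 | 0.981 | above 0.999 |

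With rho = 0.5, lowering epsilon to 0.7 gives 0.808 at 46 and 0.936 at 67. An epsilon of 0.5 gives 0.704 and 0.863.

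**The case for a change.** The best case for acting is that 33% and 60 cannot both be right, the correction is one sentence, and it costs nothing in enrolment. It can be added that an allowance for attrition means little until a rate is stated, and that the increase to 100 was an opportunity to state expected completers and power.

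The arithmetic error stands. So does the observation that power at 100 cannot be read from the text without a correlation and a loss rate. What does not stand is the inference that power is unprotected. It needs two things the plan does not say: that 33% is a dropout rate, and that 60 is the number to be enrolled. Nor does the text set a retention criterion based on 33%, so no feasibility judgement depends on the figure. The sentence about increased power is correct as written, since 100 exceeds 60.

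A second line of argument notes that controls receive the training after their 4-week data, which leaves two measurements with an untreated control. On two measurements, with rho = 0.5, power would be 0.693 at 40 completers and 0.897 at 67. Which time points give a clean comparison is a question about the design and analysis model. It would arise whatever percentage was printed here, so it adds no weight to a point about attrition arithmetic.

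**Conclusion.** The concern does not call for a change. The printed percentage is wrong by about three points (30% against 33%), which amounts to one or two participants and, for a 25% loss, 0.008 of power (0.895 against 0.903). That is a clerical slip or a rounding to a convenient total.

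It sits in a derivation that no longer sets enrolment. The current 100 exceeds each corrected figure: 62 for a literal 33% increase, and 70 if 33% is taken as the loss. Because 100 is a maximum, recruitment could fall short of it; even so, 70 enrolled would keep 46 completers after a 33% loss (70 × 0.67 = 46.9).

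The power figures rest on rho = 0.5 and epsilon = 1, which the plan does not state but which reproduce its 46. At rho = 0.3 with epsilon = 1, 67 completers still give 0.917. A severe departure from sphericity would lower power below 90% (0.863 at epsilon = 0.5), but that comes from the assumptions behind 46 and not from the attrition step. Correcting the percentage would alter nothing the trial does or concludes, and completers and power at 100 can be worked out by the analyst from observed retention.

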### **Vulnerable Populations**

---

*Please check the population(s) that will be enrolled. Check all that apply.*

Pregnant Women/Fetuses/Neonates

Minors with Parental Permission

Minors Who can Consent Themselves, emancipated minors/pregnant minors...

Prisoners

Other

None of the Above

\*required

### **Are you excluding your populations based on gender, race or ethnic origins?**

---

Yes

No

\*required

### Would your population be considered decisional/cognitively impaired?

---

Yes

No

\*required

### Recruitment

---

#### Describe how subjects will be recruited.

---

We, either the PI or research assistant (CITI-trained), will be recruiting adults aged 50 or older living in Southern Nevada. The research team will recruit 100 older adults from different senior homes or institutions that serve older adults, such as the Osher Lifelong Learning Institute (OLLI) at UNLV, with approximately equal numbers of participants (**n = 50**) in each RCT condition. Senior housing and OLLI staff will help advertise our study to their residents/members by posting flyers or emailing the flyer (they will not be involved in recruitment, data collection, or answering questions; they will direct the potential participants to us for any research-related questions). The research team will also directly work with the onsite manager of the senior apartments to post our flyers, promote our study, and recruit from the sites. Once the research team has received approval from the apartment manager, we will have a table in the lobby to recruit potential participants, we will also post flyers in the lobby area so interested participants can directly call the PI. The PI will ask the apartment complex to provide a facility authorization letter once approval to use the facility is received.

Recruitment will occur face-to-face at the older adult's apartment complex (probably in the lobby area, where we will obtain potential participants' contact information) or via phone (if potential participant call us with interest to participate). We will also use the OLLI site for recruitment, and approval to use the facility will be sought. During the recruitment phase, research team is only collecting potential participants name and contact information for screening visit.

At the end of the intervention, we will also recruit **8-10** volunteers from the study to participate in **two focus groups (each with 4-5 participants)** to further collect qualitative data on the feasibility of the study. During the final data collection at the end of the fourth week research team will ask the participants if they would like participate in a focus group interview. We will randomly choose **8-10** participants from the interested pool of the participants.

Describe the type of documents used (e.g., flyers, email, verbal announcements, etc.).

---

Study flyer will be used to advertise the study. Advertisement emails will be sent to apartment staff and OLLI staff to email it to their residents/members.

Attach recruitment materials here

---

*Attachments are required because links can be changed or removed.*

[LKM Recruitment Flyer 2023.pdf](#)

[Email script v.3.docx](#)

\*required

## **Purpose**

---

*State the purpose of the study in lay terms.*

**Note:** DO NOT copy and paste directly from your grant proposal, dissertation prospectus, clinical protocol, etc.

The purpose of the study is to examine whether the intervention (Loving kindness meditation) is feasible and acceptable among adults 50 years or older. The second aim is to examine the preliminary efficacy or impact of the intervention on reducing loneliness, depressive symptoms, and anxiety and improving compassionate love and cognitive function among this population group.

\*required

## **Objectives**

---

*Briefly describe your research questions and the objectives of this study in lay terms. State what you hope to learn from the study and assess the importance of this new knowledge. What do you aim to achieve through this research?*

**Note:** DO NOT copy and paste directly from your grant proposal, dissertation prospectus, clinical protocol, etc.

Objective 1: To evaluate the feasibility of implementing loving-kindness meditation (LKM) among older adults. Research Question 1: Is LKM intervention feasible and acceptable among older adults? We hope to find that intervention is feasible and acceptable among this population. We will also gather data on challenges and how to improve/refine this intervention for future research through a focus group interview.

Objective 2: To examine the preliminary effectiveness of the LKM in increasing positive emotions such as compassionate love. Research Question 2: What is the preliminary effect of the LKM on compassionate love? Hypothesis: Older adults will show an increased compassionate love (Self-compassion scale) after 30 days of intervention. Objective 3: To examine the preliminary impact of the LKM in reducing loneliness and improvement in cognitive function and mental health. Research Question 3: What is the preliminary effect of the LKM on loneliness, depressive symptoms, anxiety scores, and cognitive function?

Hypothesis: Older adults will show a reduced feeling of loneliness, depressive symptoms (CESD) and anxiety (PROMIS anxiety scale), and improved cognitive function (PROMIS cognitive function scale) after 30 days of intervention.

\*required

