The orientation is about 10-20 minutes (with both in person and recording) and recorded LKM training is about 30-35 minutes (video links provided under interview section as attachments). We will also have a Questions and Answers session, which could take up 10-20 minutes. Participants will be then given the link to fill out the post intervention questionnaires on their own and if they request paper and pen version, those would be available as well.

After 3 weeks of intervention, we will call to set up an appointment to meet both intervention and control group to collect data for 4 week data collection. At this data collection session, we will also collect 30-day journal folders. At this time, we will also ask for **8-10** volunteers for focus group study (we will have two group of 4-5 participants) and once we have their permission, we will set up another appointment for focus group interview, which may take up to 90 minutes at either OLLI campus or apartment's media room. We will also set up an appointment for control group for their LKM training after collecting time 2 data from them. We will do a month follow-up again at 8 week for intervention group and 4week post-intervention data collection for control group.

There are three areas of outcome measures we are aiming to determine: feasibility, acceptability, and initial efficacy:

(1) feasibility of collecting measures of self-compassion, loneliness, depressive symptoms, anxiety, and cognitive function; (2) acceptability of the intervention (i.e., satisfaction, adherence, recruitment, and retention rates); and (3) initial efficacy (i.e., changes in loneliness along with self-compassion, depressive symptoms, anxiety and cognitive function at immediately post-intervention, at 30 and 60 day follow-up). We will evaluate feasibility through participants' satisfaction, their continued use of intervention after the study completion, how appropriate the intervention was for them, their positive or negative effects associated with the intervention. We will also assess their active and continual participation, retention rates, participation rate, and missing data on collected measures. We will also conduct two focus group with **4-5 participants in each group** at the end of the study to determine the feasibility of the study and how we can further improve the intervention for future research. PI will transcribe the qualitative interviews.

\*required

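### The efficacy hypotheses and outcome definition name no comparator, and only the baseline-to-week-4 change can be compared with untrained controls

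*Combined protocol and SAP*

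**What the plan says.** In the Combined protocol and SAP, the Objectives section gives two efficacy hypotheses. For Objective 2: "Older adults will show an increased compassionate love (Self-compassion scale) after 30 days of intervention". For Objective 3: "Older adults will show a reduced feeling of loneliness, depressive symptoms (CESD) and anxiety (PROMIS anxiety scale), and improved cognitive function", again after 30 days. Neither refers to the waitlist.

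The outcome paragraph under the heading How will you conduct this study? describes initial efficacy as "changes in loneliness along with self-compassion, depressive symptoms, anxiety and cognitive function at immediately post-intervention, at 30 and 60 day follow-up". It names no between-arm contrast.

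The sample-size section takes a comparative view: "We will use a randomized controlled trial (RCT) with waitlist control to determine the intervention's feasibility, acceptability, and initial efficacy". It sizes the trial "for a repeated measure ANOVA between-within effects, with two groups and four measurement time points, the sample size was determined to be 46". The four times listed there are baseline, right after the intervention, one month and the second month, so they are set relative to the intervention.

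The procedures text adds one control-arm measurement at week 4, before the controls are trained. It describes the week-8 visit as follow-up for the LKM arm and as a four-week post-training visit for the controls. The supplied text has no separate efficacy analysis section.

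**The concern.** A waitlist arm is there to separate the effect of LKM from change that would have happened anyway. Self-reported loneliness, mood and anxiety can move on repeat measurement without treatment. A hypothesis that says only that people will change after 30 days is met by such movement, even if the waitlist moves just as far.

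Naming the waitlist would not be enough on its own, because it is an untrained comparator at one follow-up time only. If efficacy is claimed at all three listed times, two of those claims cannot rest on a randomised contrast with untrained people. At stake is whether the preliminary efficacy result can be attributed to LKM.

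**Working it through.** **1. The plan's own figure.** Stated inputs (sample-size section): f = 0.2, "an alpha of 0.05, and a power of 90"%, two groups, four times. Assumed, because not stated: correlation ρ = 0.5 between times, and sphericity. For the group-by-time interaction, λ = f²·N·m/(1−ρ), with df1 = (2−1)(m−1) and df2 = (N−2)(m−1).

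- N = 46, m = 4: λ = 0.04 × 46 × 4 / 0.5 = 14.72, df 3 and 132, power 0.903. The stated 46 is reproduced.
- With ρ = 0.3 the requirement would be 64; with ρ = 0.7 it would be 28.
- A pure time effect at ρ = 0.5 also gives 46, so the number alone does not identify the test. The wording about between-within effects in two groups does, and it points to a comparison of change between arms.

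**2. Which times have an untrained comparator** (from the procedures text):

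| Time | LKM arm | Waitlist arm | Untrained comparator |
|---|---|---|---|
| Baseline | untrained | untrained | both arms untrained |
| Immediately post | just trained | measured only after own, later training | none |
| Week 4 (30 days) | trained | extra measurement before training | yes |
| Week 8 (60 days) | trained | four weeks after own training | none |

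If the four-time ANOVA is aligned on each person's own training, every control follow-up in it is a trained one. If it is aligned on the calendar, the controls have no immediately-post value and their week-8 value is a trained one. Neither alignment gives a four-time contrast with untrained controls.

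**3. Size of the risk from an uncontrolled reading (illustration).** The documents give no drift and no correlation. Assume no true LKM effect, favourable drift d in everyone, ρ = 0.5, and a two-sided 5% paired t test in the 50 LKM participants. The SD of change is √(2(1−0.5)) = 1, and the noncentrality is d√50.

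| Drift d (SD) | Noncentrality | Chance of significant improvement, ρ = 0.5 | Same, ρ = 0.7 |
|---|---|---|---|
| 0 | 0 | 2.5% | 2.5% |
| 0.1 | 0.71 | 10% | 14% |
| 0.2 | 1.41 | 28% | 43% |
| 0.3 | 2.12 | 55% | 77% |

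In a between-arm comparison of change, drift common to both arms cancels (d − d = 0), so the rate in the favourable direction stays at 2.5%.

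**4. Power of the clean contrast.** Same formula, m = 2 (baseline and week 4), f = 0.2, ρ = 0.5.

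- N = 100: λ = 0.04 × 100 × 2 / 0.5 = 16, df 1 and 98, power 0.977 (0.917 at ρ = 0.3, 0.999 at ρ = 0.7).
- N = 60: λ = 9.6, power 0.861.
- Four-time test at N = 100: λ = 32, df 3 and 294, power 0.999.

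With two groups and two times each cell's interaction effect is ±δ/4, where δ is the between-arm difference in change. So f = 0.2 means δ = 4 × 0.2 = 0.8 SD. Check: the standard error is √(2(1−0.5)(1/50 + 1/50)) = 0.2, and (0.8/0.2)² = 16.

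**The case against.** The strongest reply is that the design already supplies the comparator. The sample-size section says the waitlist trial is used to determine initial efficacy, and the only test named anywhere is a two-group one. The Objectives field asks for lay terms, and the efficacy phrase in the outcome paragraph is a list of variables and times, not a decision rule. The extra week-4 control visit has an evident use as an untrained comparator.

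Much of this stands. A reader might infer that the trial intends to count uncontrolled pre-to-post change as efficacy, or to pool both arms' trained months into one paired test. The documents do not support either inference: no paired test and no pooling is proposed, and the sizing is comparative. A reader might also infer that results will be biased towards benefit. That too goes beyond the documents, which give neither the size nor the direction of any drift.

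Two things survive. The outcome paragraph is not a lay-terms field and has the same omission. And comparative intent cannot supply an untrained comparator immediately post or at 60 days, because the schedule provides none.

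**Conclusion.** The point holds as an inconsistency with a practical consequence. The hypotheses and the definition of initial efficacy do not match the comparative basis in the sample-size section. Of the three efficacy times listed, only week 4 allows a randomised comparison with untrained controls. Efficacy claimed immediately post or at 60 days, or from the four-time ANOVA with times set relative to the intervention, could reflect uncontrolled change or compare trained with trained.

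The 10% to 55% range shows how far an uncontrolled reading could mislead under assumed drift of 0.1 to 0.3 SD and correlation 0.5; it does not predict this trial. The power of about 0.98 assumes 100 analysed, correlation 0.5, and the plan's f = 0.2 carried over to two times, which is a 0.8 SD difference in change. The timing argument depends on neither calculation. It rests on the supplied text; the schedule of assessments is listed as an attachment and was not available to check. This is a cheap improvement, not a flaw in the design.

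**What to change.** - **Objectives.** State both hypotheses with the comparator: from baseline to week 4, participants assigned to LKM will show a greater increase in self-compassion, greater reductions in loneliness, depressive symptoms and anxiety, and a greater improvement in cognitive function than participants assigned to the waitlist.
- **Outcome paragraph under How will you conduct this study?** Define initial efficacy as the between-arm difference in change from baseline to week 4, using the controls' measurement taken before their training.
- **Other times.** Report the immediately-post changes, the 60-day changes and the controls' post-training changes as descriptive within-group estimates with intervals, and make no efficacy claim from them.

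**Cost.** Wording in the next modification, with no new visits or data. Within-group improvements and the later time points can no longer be cited as evidence of efficacy. The two-time contrast has slightly less nominal power than the four-time test (about 0.98 against 0.999 at N = 100, f = 0.2, assumed correlation 0.5), although the four-time figure does not belong to a clean comparison with untrained controls.
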